10.9.8.7.1. Prohibited During the Study

Receipt of the following vaccines and medications during the time periods listed below may exclude a participant from the per-protocol analysis from that point onward; however, it is anticipated that the participant would not be withdrawn from the study (Section 7). Medications and vaccinations should not be withheld if required for a participant's medical care.

- Investigational vaccines and investigational drugs are prohibited within 28 days prior to enrollment and thereafter during the course of the study.
- Licensed or nonstudy investigational RSV vaccines are prohibited at any time prior to study enrollment and thereafter during the course of the study.
- Nonstudy investigational influenza vaccines are prohibited at any time prior to study enrollment and thereafter during the course of the study.
- Licensed influenza vaccines are prohibited ≤120 days before study intervention administration and thereafter during the course of the study.
- Nonstudy inactivated or recombinant vaccines, licensed COVID-19 vaccines, or COVID-19 vaccines authorized for temporary or emergency use are prohibited within 14 days after study intervention administration.
- Nonstudy live vaccines should not be given within 28 days prior to enrollment and thereafter during the course of the study.
- Chronic systemic treatment with known immunosuppressant medications, or radiotherapy, is prohibited within 60 days prior to enrollment thereafter during the course of the study.
- Systemic corticosteroids (≥20 mg/day of prednisone or equivalent) for ≥14 days are prohibited within 28 days prior to enrollment and thereafter during the course of the study.
- Blood/plasma products or immunoglobulins are prohibited within 60 days prior to enrollment and thereafter during the course of the study.
- Prophylactic antipyretics and other pain medication to prevent symptoms associated with study intervention administration are not permitted. However, if a participant is taking a medication for another condition, even if it may have antipyretic or pain-relieving properties, it should not be withheld prior to study vaccination.

10.9.8.7.2. Permitted During the Study

- Medication other than that described as prohibited in Section 10.9.8.7.1 required for treatment of preexisting conditions or acute illness is permitted.
- Inhaled/nebulized, intra-articular, intrabursal, or topical (eg, skin, eyes, ears) corticosteroids are permitted.

The use of antipyretics and other pain medication to treat symptoms associated with study intervention administration is permitted.

10.9.9. Discontinuation of Substudy A Intervention and Participant Discontinuation/Withdrawal

See Section 7.

10.9.10. Substudy A Assessments and Procedures

10.9.10.1. Immunogenicity Assessments

10.9.10.1.1. Blood Collection

Blood samples (approximately 50 mL per sample) for immunogenicity assessments will be collected from all enrolled participants just prior to each study vaccination at Visit A101 and Visit A102, and at Visit A103. The total blood sampling volume for individual participants in this study is approximately 150 mL across 2 months.

Instructions for the collection and handling of blood and serum samples will be provided in the laboratory manual. The date and time of each sample will be recorded.

The immunogenicity samples must be processed and shipped as indicated in the instructions provided to the investigator site to maintain sample integrity. Any deviations from the immunogenicity sample handling procedure (eg, sample collection and processing steps, interim storage, or shipping conditions), including any actions taken, must be documented, and reported to the sponsor. On a case-by-case basis, the sponsor may make a determination as to whether sample integrity has been compromised.

10.9.10.1.2. RSV Vaccine Antibody Testing

Serum samples collected at all 3 visits will be assayed for RSV A and RSV B serum NTs.

RSV A and RSV B serum NTs will be determined and reported as the NT at each blood sampling visit.

Sample collection, processing, storage, and shipping information can be found in the laboratory manual. All assays will be performed by Pfizer and/or at a facility designated by Pfizer.

10.9.10.1.3. qIRV Immune Response Testing

Serum samples collected at Visit A101 and Visit A102 will be assayed for seasonal influenza strains (2×A, 2×B) as recommended by WHO for recombinant or cell-based influenza assays.

Immune response testing for seasonal strains (2×A, 2×B) will be assessed by strain-specific HAI antibody titers to evaluate vaccine responses.

Sample collection, processing, storage, and shipping information can be found in the laboratory manual. All assays will be performed by Pfizer and/or at a facility designated by Pfizer.

10.9.10.1.4. Exploratory Assays, Including Immunogenicity Assessments and Assay Development

Samples remaining after completion of the planned assays from blood draws may be used for additional vaccine and infectious disease-related research. Samples may also be used for assay development, standardization, qualification, and validation. This work is critical in the development, qualification, and validation of serological assays and is required by regulatory authorities for their use in the licensure of a vaccine.

10.9.10.2. Biological Samples

See Section 8.2.3.

10.9.10.3. Safety Assessments

See Section 8.3.

10.9.10.4. Adverse Events, Serious Adverse Events, and Other Safety Reporting

See Section 8.4.

10.9.10.5. Stopping Rules

The following stopping rules are in place for Substudy A participants, based on review of AEs, ECG, and laboratory data, and apply to Vaccination 1, Day 1 through Day 28. These data will be monitored on an ongoing basis by the investigator (or medically qualified designee) and sponsor in order to promptly identify and flag any event that potentially contributes to a stopping rule. In the event that sponsor personnel confirm that a stopping rule is met, the following actions will commence:

- The IRC will review all appropriate data.
- The stopping rule will PAUSE randomization and any further administration of Vaccination 1 (RSVpreF + qIRV or qIRV). The PAUSE will not apply to those participants who received Vaccination 1 prior to the stopping rule being met.

 For those participants already vaccinated, all routine study conduct activities, including ongoing data entry, reporting of AEs, participant e-diary completion, blood sample collection, and participant follow-up, will continue during the pause.

A stopping rule is met if any of the following criteria occur within 28 days after receiving Vaccination 1 (RSVpreF + qIRV or qIRV).

10.9.10.5.1. Stopping Rule Criteria

If any participant vaccinated with qIRV or RSVpreF + qIRV develops:

- A new ECG abnormality that a cardiologist judges consistent with probable or possible myocarditis or pericarditis, including:
 - Sustained atrial or ventricular arrhythmias.
 - Second-degree Mobitz Type II or worse AV block or new bundle branch block.
 - Diffuse ST-segment elevation or PR-segment inversion, compatible with pericarditis.
- An abnormal troponin I value that is confirmed to be abnormal on repeat testing, assessed as related to study intervention by the investigator.
- If ≥1 participant vaccinated with qIRV or RSVpreF + qIRV develops confirmed myocarditis or pericarditis.
- If any participant vaccinated with qIRV or RSVpreF + qIRV dies.
- If ≥1 participant vaccinated with qIRV or RSVpreF + qIRV experiences a Grade 4 unsolicited AE, or SAE of any severity, assessed as related by the investigator.
- 6. If ≥2 participants vaccinated with qIRV or RSVpreF + qIRV develop the same or similar Grade 3 or higher (see Section 10.3.3, Assessment of Intensity) unsolicited AE (including laboratory abnormalities, except lymphocyte count and C-reactive protein), other than myocarditis/pericarditis, assessed as related to study intervention by the investigator.

Note that the local reactions, systemic events, and fever (Section 8.3.4) reported within 7 days from the day of administration of Vaccination 1, irrespective whether they are recorded in the e-diary or as AEs, are excluded from this stopping rule.

A charter for the IRC will be prepared and finalized before the first participant is consented.

10.9.10.6. Study Procedures

10.9.10.6.1. Visit A101 – Vaccination 1 (Day 1)

Before enrollment and before any study-related procedures are performed, voluntary, written study-specific informed consent will be obtained from the participant. Each signature on the ICD must be personally dated by the signatory. The investigator or his or her designee will also sign and date the ICD. A copy of the signed and dated ICD must be given to the participant. The source data must reflect that the informed consent was obtained before participation in the study.

Study procedures should be conducted in a stepwise manner as shown below:

- Obtain written informed consent either in electronic or hard-copy format from the participant before performing any study-specific procedures.
- Assign a single participant identifier using the IRT system.
- Obtain and record the participant demography (including complete date of birth [dd-Mmm-YYYY], sex, race, racial designation, and ethnicity). The full date of birth will be collected to critically evaluate the immune response and safety profile by age.
- Obtain and record any medical history of clinical significance. Include date of onset and resolution (if applicable). Use best estimate if unknown.
- Perform a clinical assessment. If the clinical assessment indicates that a physical
 examination is necessary to comprehensively evaluate the participant, perform a physical
 examination and record any findings in the source documents and, if clinically
 significant, record on the medical history CRF (Section 8.3.1).
- Measure the participant's vital signs, including blood pressure (seated) and pulse rate.
- Measure the participant's prevaccination body temperature (oral or tympanic) to ensure that the temperature is not ≥38°C.
- Discuss contraceptive use where applicable and as described in Section 5.3.1.
- Collect details (when available) of any licensed influenza vaccine received in the last 12 months prior to enrollment in the study. Include product name and date of administration.
- Record any nonstudy vaccinations received prior to Visit A101 as described in Section 10.9.8.7. Include product name and date of administration.
- Review concomitant medication use and record any medications that are prohibited, as described in Section 10.9.8.7.1.
- Ensure and document that all the inclusion criteria and none of the exclusion criteria are met.
- Ensure that the participant does not meet any temporary delay criteria as described in Section 5.5.

Note: If delay criteria are met, reschedule Vaccination 1 for a later date when the reason(s) for the temporary delay have resolved. Randomization, Visit A101 study intervention assignment in the IRT, and blood collection are to be deferred until the participant returns for Vaccination 1.

- Prior to vaccination, collect a blood sample of approximately 50 mL for immunogenicity testing.
- Obtain the participant's randomization number and Visit A101 study intervention assignment using the IRT system.
- Unblinded site staff member(s) will dispense/administer the assigned study intervention into the deltoid muscle as detailed in Section 6.2.1. Please refer to the IPM for further instruction on this process.
- Blinded site staff must observe the participant for at least 30 minutes after study
 intervention administration for any acute reactions. Record any acute reactions (including
 time of onset) in the participant's source documents and on the AE page of the CRF, and
 on an SAE form, if applicable.
- Explain the e-diary technology and completion requirements. Assist with installing the
 e-diary application onto the participant's own device or, if required, issue a sponsorprovisioned e-diary.
- Issue a measuring device to measure local reactions at the injection site and a thermometer for recording oral temperature.
- Ensure that the participant is comfortable with the chosen e-diary platform, confirm
 instructions on e-diary completion, and ask the participant to complete the e-diary from
 Day 1 through Day 7, where Day 1 is the day of Vaccination 1.
- Ask the participant to contact the site staff or investigator immediately if he or she
 experiences any of the following from Day 1 through Day 7 after vaccination (where Day
 1 is the day of vaccination) to determine if an unscheduled reactogenicity visit is
 required:
 - Fever ≥39.0°C (≥102.1°F).
 - Redness or swelling at the injection site measuring greater than 10 cm (>20 measuring device units).
 - Severe pain at the injection site.
 - Any severe systemic event.
- If the participant doesn't call, the site should contact the participant to determine if an
 unscheduled reactogenicity visit is required.
- Request that the participant bring their completed e-diary device to the next visit.
- Ask the participant to contact the site staff or investigator immediately if the participant experiences acute chest pain, shortness of breath, or palpitations (see Section 10.9.10.6.4.2).

- Record AEs and SAEs as described in Section 10.3.3 and obtain and record stop dates for previously reported events.
- Schedule an appointment for the next study visit.
- Complete the source notes and CRF.

Final Protocol Amendment 1, 30 May 2023

- The investigator or an authorized designee completes the CRFs and an unblinded dispenser/administrator updates the study intervention accountability records.
- The investigator or appropriately qualified designee reviews the reactogenicity e-diary data online following vaccination to evaluate participant compliance and as part of the ongoing safety review. Daily review is optimal during the active diary period.

10.9.10.6.2. Visit A102 - Vaccination 2 (28-35 Days After Vaccination 1)

- Perform a clinical assessment. If the clinical assessment indicates that a physical examination is necessary to comprehensively evaluate the participant, perform a physical examination and record any findings in the source documents and, if clinically significant, record as an AE (Section 8.3.1).
- Measure the participant's prevaccination body temperature (oral or tympanic) to ensure that the temperature is not ≥38°C.
- Discuss contraceptive use where applicable and as described in Section 5.3.1.
- Record any nonstudy vaccinations received prior to Visit A102 as described in Section 10.9.8.7. Include product name and date of administration.
- Review concomitant medication use and record any medications that are prohibited, as described in Section 10.9.8.7.1.
- Ensure and document that all the inclusion criteria and none of the exclusion criteria are met. If the participant is no longer eligible, follow-up actions are described in Section 7.1.
- Ensure that the participant does not meet any temporary delay criteria as described in Section 5.5.
 - Note: If delay criteria are met, reschedule Vaccination 2 for a later date when the reason(s) for the temporary delay have resolved. Randomization, Visit A102 study intervention assignment in the IRT, and blood collection are to be deferred until the participant returns for Vaccination 2.
- Prior to vaccination, collect a blood sample of approximately 50 mL for immunogenicity testing.
- Obtain the participant's Visit A102 study intervention assignment using the IRT system.
- Unblinded site staff member(s) will dispense/administer the assigned study intervention into the deltoid muscle as detailed in Section 6.2.1. Please refer to the IPM for further instruction on this process.

- Blinded site staff must observe the participant for at least 30 minutes after study
 intervention administration for any acute reactions. Record any acute reactions
 (including time of onset) in the participant's source documents and on the AE page of
 the CRF, and on an SAE form as applicable.
- Review the e-diary technology and completion requirements. Assist with installing the
 e-diary application onto the participant's own device or, if required, issue a
 sponsor-provisioned e-diary.
- If required, reissue a measuring device to measure local reactions at the injection site and a thermometer for recording oral temperature.
- Ensure that the participant remains comfortable with the chosen e-diary platform, confirm instructions on e-diary completion, and ask the participant to complete the e-diary from Day 1 through Day 7, where Day 1 is the day of Vaccination 2.
- Ask the participant to contact the site staff or investigator immediately if he or she
 experiences any of the following from Day 1 through Day 7 after vaccination to
 determine if an unscheduled reactogenicity visit is required:
 - Fever ≥39.0°C (≥102.1°F).
 - Redness or swelling at the injection site measuring greater than 10 cm (>20 measuring device units).
 - Severe pain at the injection site.
 - Any severe systemic event.
- If the participant doesn't call, the site should contact the participant to determine if an
 unscheduled reactogenicity visit is required.
- Request that the participant bring their completed e-diary device to the next visit.
- Obtain stop dates for any ongoing events recorded on the last day of e-diary completion for the previous period.
- Record AEs and SAEs as described in Section 10.3.3 and obtain and record stop dates for previously reported events.
- Schedule an appointment for the next study visit.
- The investigator or an authorized designee completes the CRFs and an unblinded dispenser/administrator updates the study intervention accountability records.
- The investigator or appropriately qualified designee reviews the reactogenicity e-diary data online following vaccination to evaluate participant compliance and as part of the ongoing safety review. Daily review is optimal during the active diary period.

10.9.10.6.3. Visit A103 - Follow-Up Visit (28-35 Days After Vaccination 2)

- Record any nonstudy vaccinations received since the last study visit as described in Section 10.9.8.7.
- Review concomitant medication use and record any medications that are prohibited, as described in Section 10.9.8.7.1.
- Collect a blood sample of approximately 50 mL for immunogenicity.
- Review the e-diary data and obtain stop dates for any ongoing events recorded on the last day of e-diary completion for the previous period.
- Record AEs and SAEs as described in Section 10.3.3 and obtain and record stop dates for previously reported events.
- Collect the sponsor-provisioned e-diary or assist the participant with removing the study
 application from his or her own personal device. Ensure that all data have been
 transferred before deactivating the e-diary or deleting the app.
- Complete the CRF and source documents.

10.9.10.6.4. Early Withdrawals – Safety Follow-Up (28-35 Days After Last Vaccination Received)

- Safety follow-up may be conducted via a phone call, or a site visit if a blood draw is required.
- For participants who received study intervention at the visit prior to withdrawal, collect the immunogenicity 50-mL blood sample and process it as indicated in the laboratory manual.
- Review the e-diary data and obtain and record stop dates for any ongoing events recorded on the last day of e-diary completion for the previous period(s).
- Record AEs and SAEs as described in Section 10.3.3 and obtain and record stop dates for previously reported events.
- Collect the sponsor-provisioned e-diary or assist the participant with removing the study application from his or her own personal device.
- Complete the CRF and source documents.

10.9.10.6.4.1. Unscheduled Reactogenicity Visits for a Grade 3 or Suspected Grade 4 Reaction

If a severe local reaction (Section 8.3.4.2), severe systemic event (Section 8.3.4.3), or fever ≥39.0°C (≥102.1°F) (Section 8.3.4.4) is reported in the e-diary, a telephone contact with the participant should occur to ascertain further details and determine whether a site visit is clinically indicated. If a suspected Grade 4 local reaction, systemic event, or fever is reported in the reactogenicity e-diary, a telephone contact or site visit should occur to confirm whether the event meets the criteria for Grade 4.

A site visit or referral to a healthcare facility should be scheduled as soon as possible to assess the extent of the reaction, unless:

- The participant is unable to attend the unscheduled visit, or
- The reaction is no longer present at the time of the contact, or
- The participant recorded an incorrect value in the e-diary (confirmation of an e-diary data entry error), or
- The investigator or appropriate designee determines that an unscheduled visit is not required.

This contact will be recorded in the participant's source notes and in the CRF.

If the participant is unable to attend the unscheduled visit, or the investigator or authorized designee determines it is not needed, any ongoing local reactions/systemic events must be assessed at the next study visit.

The reactogenicity events should be assessed by the investigator or a medically qualified member of the site staff, such as a study physician or a study nurse, as applicable to the investigator's local practice or healthcare facility, who will:

- Measure body temperature (°C/°F).
- If present, measure the minimum and maximum diameters of redness at the injection site.
- If present, measure the minimum and maximum diameters of swelling at the injection site.
- Assess the injection site pain in accordance with the reactogenicity grading scale provided in Section 8.3.4.2.
- Assess any systemic events (fatigue, headache, vomiting, nausea, diarrhea, chills, new or worsened muscle pain, or new or worsened joint pain) that are present in accordance with the reactogenicity grading scale provided in Section 8.3.4.3.
- Assess for other findings associated with the reaction and record on the AE CRF, if appropriate.
- Record AEs and SAEs as described in Section 8.4.
- Complete the participant's source documents.
- The investigator or an authorized designee completes the unscheduled visit assessment CRF.

10.9.10.6.4.2. Additional Procedures for Monitoring of Potential Myocarditis or Pericarditis

Any study participant who reports acute chest pain, shortness of breath, palpitations, or any other symptom(s) that might be indicative of myocarditis or pericarditis within 28 days after Vaccination 1 must be specifically evaluated for possible myocarditis or pericarditis.

In addition to a clinical evaluation, the following should be performed:

- ECG and
- Measurement of the troponin level

If myocarditis or pericarditis is suspected based upon the initial evaluation, the following should also be performed:

- Evaluation by a cardiologist,
- Cardiac echocardiogram, and/or
- Cardiac magnetic resonance study

Details of the symptoms reported, and results of the investigations performed, will be recorded in the CRF.

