9.3.1. General Considerations

CIs for all endpoints in the statistical analysis will be presented as 2-sided at the 95% level unless specified otherwise.

The safety analyses are based on the safety population. Participants will be summarized by vaccine group according to the study interventions they actually received. Missing AE dates will be imputed according to Pfizer safety rules.

Completely missing e-diary data (ie, all 7 days of e-diary collection were missing) will not be imputed. For partially complete e-diary data (ie, 1-6 days of reactogenicity data are available), it is assumed that no reactions or events were experienced on missing days based on the e-diary data source. For participants with e-diary data transmitted, related reactogenicity data reported within 7 days after vaccination may be included in the analysis.

For all the immunogenicity endpoints, the analysis will be based on the evaluable immunogenicity population(s). An additional analysis may be performed based on the mITT population. Participants will be summarized according to the group to which they were randomized

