3.1.3. Primary Safety Endpoints

In general, e-diary data that are confirmed as errors will not be used for derivation or analysis.

Feedback was received from the FDA on reactogenicity data collection and analysis. Most recently, the FDA stated the concern of missing e-diary entries for reactogenicity events. However, Pfizer sends reminders to sites to follow up on missing e-diary entries, and the reminders are also sent to sites from the vendor. Also, CRF completion guidelines do allow sites to enter e-diary events into the AE CRF. Therefore, Pfizer uses both sources for the reactogenicity data: the e-diary and the AE CRF. Since the AE CRF did not designate a specific page to collect reactogenicity data that were missing in the e-diary, Pfizer has adopted a process of providing a listing of AEs reported within 7 days after vaccination to the clinical team to review/query the AEs, and to finalize the PTs that should be considered reactogenicity before the database lock. For the AEs reported on the same day of vaccination but missing the AE start time, these AEs are defaulted to be considered AEs after vaccination. Then any AEs reported within 7 days after vaccination that match with those flagged PTs, (either "related," or unrelated as assessed by the investigator) will be pooled with reactogenicity data from the e-diary. If the same reactogenicity is reported on the same day from both the e-diary and the AE CRF, the highest grade from the 2 data sources will be used for that specific day.

> DMB02-GSOP-RF02 7.0 Statistical Analysis Plan Template 31-Jan-2022 PFIZER CONFIDENTIAL TMF Doc ID: 98.03 Page 17 of 46

It should be noted that the data collection in the AE CRF is different from that of the e-diary:

- For redness, swelling, and fever, the measured size of redness and swelling at the injection site and temperature are recorded in the e-diary, but not in the AE CRF. Therefore, the maximum grading for the 3 items reported in the e-diary will be based on actual size and the FDA toxicity grading scale, but the maximum grading of the 3 reactogenicity terms from the AE CRF will be based on the grading scale on the CRF page. For the 7 days, only the maximum grading from both sources will be used for the aggregated severity analysis, though the grading algorithm is different between the 2 data sources.

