3.1.3.1.2. Maximum Severity of Local Reactions Within 7 Days After Vaccination

The grading of local reactions is listed in Table 5.

 Table 5.
 Grading Scale for Local Reactions

	Mild Grade 1	Moderate Grade 2	Severe Grade 3 ^a	Grade 4 ^b
Redness	2.5 cm to 5.0 cm	>5.0 cm to 10.0 cm	>10 cm	Necrosis or exfoliative
	(5 to 10 measuring	(11 to 20 measuring	(>20 measuring	dermatitis
	device units from	device units from the	device units from	
	the e-diary) or mild	e-diary) or moderate	the e-diary) or	
	from the AE CRF.	from the AE CRF.	severe from the AE	
			CRF.	

DMB02-GSOP-RF02 7.0 Statistical Analysis Plan Template 31-Jan-2022 PFIZER CONFIDENTIAL TMF Doc ID: 98.03 Page 20 of 46

	Mild	Moderate	Severe	Grade 4 ^b
	Grade 1	Grade 2	Grade 3 ^a	
Swelling	2.5 cm to 5.0 cm	>5.0 cm to 10.0 cm	>10 cm	Necrosis
_	(5 to 10 measuring	(11 to 20 measuring	(>20 measuring	
	device units from	device units from the	device units from	
	the e-diary) or mild	e-diary) or moderate	the e-diary) or	
	from the AE CRF.	from the AE CRF.	severe from the AE	
			CRF.	
Pain (at the	Does not interfere	Interferes with	Prevents daily	Emergency room visit or
injection site)	with activity (mild	activity (moderate	activity (severe	hospitalization for severe
	from the e-diary or	from the e-diary or	from the e-diary or	pain at the injection site.
	the AE CRF).	the AE CRF).	the AE CRF).	

 Table 5.
 Grading Scale for Local Reactions

a. The maximum reaction size in measuring device units is 21 (10.5 cm). Any reaction size >21 measuring device units is recorded as a number that is >20 (eg, 21) in the e-diary.

b. Grade 4 assessment should be made by the investigator using the AE severity grading scale. The assessment will be collected on the AE CRF and thus not reported from the e-diary.

The following variables are derived for each participant included in the reactogenicity subset:

1. Maximum severity of each local reaction on any day (Day 1 through Day 7).

The maximum severity (highest grading) of each local reaction within 7 days after vaccination will be derived. The maximum severity will be derived as follows:

= Missing, if values are missing for all days (Day 1 through Day 7).

= 0, if the participant reports all reactions as "no" or a combination of missing and "no" for all days (Day 1 through Day 7).

= *Highest grade* (maximum severity) within 7 days after vaccination, if the answer is not "no" for at least 1 day.

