If a participant reports a fever (or severity of fever) by mistake, the correct temperature will be transcribed in a data-handling memo to be included in the analysis, and the temperature that is confirmed as incorrect will not be included in the analysis.

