6.1.3.1. Main Analysis

- Estimand strategy: Treatment policy (Section 2.2.1.3.1).
- Analysis set: Safety population (Section 4).
- Analysis methodology: 95% CIs of the proportion of participants reporting each event will use the Clopper-Pearson method (Section 5.2.1).
- Intercurrent events and missing data: All data collected are included; partially missing diary data are imputed as "no" (Section 5.3.1.1); e-diary data that are confirmed as errors will not be used for analysis.
- Descriptive statistics, including the proportion (%), the numerator (n) and the denominator (N) used in the proportion calculation, and the 95% CI for percentage using the Clopper-Pearson method, will be presented for each vaccine group for each vaccination.
- Bar charts with the proportions of participants for each and any local reaction and each and any systemic event throughout the 7 days will be plotted for each vaccine group for each vaccination. The bars will be divided into severity categories to highlight the proportions of participants by maximum severity.

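### E-diary values confirmed as entry errors are dropped, and a replacement rule exists only for fever, so a real reaction entered with the wrong grade or size can be scored as absent

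*Protocol*

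**What the plan says.** **How an error is found.** Protocol 10.9.10.6.4.1 (Substudy A) and 10.10.10.6.3.1 (Substudy B) call for telephone contact after an e-diary report of a severe local reaction, a severe systemic event or fever of at least 39.0°C. Among the reasons for not arranging a visit is "The participant recorded an incorrect value in the e-diary (confirmation of an e-diary data entry error". On documentation: "This contact will be recorded in the participant's source notes and in the CRF". Neither section tells the site to capture the correct grade or size.

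**What the SAP does with it.** SAP 3.1.3: "In general, e-diary data that are confirmed as errors will not be used for derivation or analysis". SAP 6.1.3.1 repeats the rule next to the rule for gaps: "partially missing diary data are imputed as 'no' (Section 5.3.1.1); e-diary data that are confirmed as errors will not be used for analysis". SAP 6.1.6 carries this presentation to Substudy B.

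**How gaps are scored.** Protocol 9.3.1, on partially complete diaries: "it is assumed that no reactions or events were experienced on missing days based on the e-diary data source". SAP Tables 3 and 4 code any-day presence as No when the seven days are a mix of no and missing. SAP 3.1.3.1.2 sets maximum severity to 0 "if the participant reports all reactions as 'no' or a combination of missing and 'no' for all days". SAP 3.1.3.2 handles systemic events in a similar way.

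**The exception.** For a fever, or a fever severity, reported by mistake, SAP 3.1.3.2 says "the correct temperature will be transcribed in a data-handling memo to be included in the analysis". The SAP has no counterpart for redness, swelling, injection-site pain or the eight other systemic events. SAP 5.3.1.1 plans no sensitivity analysis of reactogenicity.

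**The concern.** A confirmed entry error can mean two things: nothing happened, or something happened and its grade or size was entered wrongly. Scoring the gap as no reaction suits the first case and is wrong in the second. The fever rule shows that the sponsor saw the second case, because it names mistaken severity as well as mistaken presence and restores the true value. The other prompted items get the deletion without the restoration.

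Presence and maximum severity of local reactions and systemic events within 7 days are primary safety endpoints in both substudies. Substudy B exists to choose between two formulations whose local tolerability may differ. The stake is therefore the accuracy of a descriptive primary summary, one participant at a time.

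**Working it through.** **Step 1: apply the derivation rules to single participants.** The code is 0 = no, 1 = mild, 2 = moderate, m = value dropped as a confirmed error. Any-day presence is Yes if any day is above 0. Otherwise it is No, provided at least one day is non-missing. Maximum severity is the highest non-missing grade.

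| Case, for one reaction | Days 1–7 under the SAP | SAP result | Result if corrected as for fever |
|---|---|---|---|
| True mild on Day 2 only, entered as severe | 0 m 0 0 0 0 0 | No, grade 0 | Yes, grade 1 |
| True moderate on Day 2 entered as severe, true mild on Day 3 | 0 m 1 0 0 0 0 | Yes, grade 1 | Yes, grade 2 |
| Nothing occurred, accidental entry on Day 2 | 0 m 0 0 0 0 0 | No, grade 0 | No, grade 0 |
| The dropped value is the only one for that reaction | m on all days with data | Missing | True value |

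Row 1 is the defect: a real reaction scored as absent. In row 2 presence survives but severity is too low, onset moves from Day 2 to Day 3, and duration can shorten. In row 3 the SAP rule is right. In row 4 the result is missing, not No. A size error behaves the same way: 12 device units (12 × 0.5 = 6.0 cm, moderate) entered as 21 (above 10 cm, severe).

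**Step 2: look for another source.** SAP 3.1.3 uses two sources, the e-diary and the AE CRF.

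- AE CRF: SAP 3.1.3 says sites are allowed to enter e-diary events there, not that they must. Protocol 8.3.4 says e-diary data are not reported in the CRF as AEs. Protocol 9.3.1 says only that related reactogenicity data may be included.
- Unscheduled-visit form: "The investigator or an authorized designee completes the unscheduled visit assessment CRF" applies when a visit takes place. A confirmed entry error is a reason for no visit, and the SAP does not name this form as a reactogenicity source.

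**Step 3: size.** The shift per lost participant is 100/n percentage points.

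| Denominator | Shift |
|---|---|
| Substudy A group, n=125 | 100/125 = 0.8 |
| Substudy B group, n=100 | 100/100 = 1.0 |
| Substudy B age-group cell, n=50 | 100/50 = 2.0 |

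Examples with Clopper-Pearson 95% CIs: 45/50 = 90.0% (78.2 to 96.7) becomes 44/50 = 88.0% (75.7 to 95.5). 90/100 = 90.0% (82.4 to 95.1) becomes 89/100 = 89.0% (81.2 to 94.4).

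**Step 4: the plan's own figure on this endpoint.** Protocol 10.10.11.5 gives 82% power for 65% versus 90% with at least 1 local reaction, 50 per group, Fisher exact test. Exact enumeration at two-sided 0.05 (the level is assumed, since the section does not state one) gives 82.03%, so the figure reproduces. It is context only; nothing above depends on it.

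**The case against.** **The AE CRF can rescue the case.** This partly stands. The clinical team reviews AEs within 7 days of vaccination before database lock, and flagged terms are pooled whether or not judged related. The reason Protocol 8.3.4 gives for keeping e-diary data out of the AE pages is duplication, and a voided entry leaves nothing to duplicate. But the route is optional, and a site reading 8.3.4 plainly would not use it. It will recover some cases without closing the gap.

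**The step from not used to missing is inferred.** This stands as a caveat. SAP 3.1.3 opens its rule with a general qualifier, and SAP 5.3.1.1 treats a transferred day as complete, so it does not address a single voided item. SAP Table 6 would leave that item missing for the day; the No arises in the any-day and maximum-severity variables. The data-handling memo and CRF guidelines may say more, but they are not in these documents.

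**Telephone recall is weaker than a same-day entry.** This is a fair cost, small over a few days, and flagging deals with it.

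Three stronger readings are tempting, and the documents do not support them:

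- *Substudy B loses power.* With 50 per group and reactors lost from the 0.5-mL group only, the planning power falls to 77.5%, 72.7% or 67.5% for losses of 1, 2 or 3 points. Those losses are invented, and sparing the 1.0-mL group is arbitrary: losing 1% of reactors in both groups gives 80.0%. At the full 100 per group the power is 98.9%. Above all, Protocol 10.10.11.1 and SAP 5.1 state no hypothesis, and reactogenicity is summarised with per-group intervals.
- *Deletions run in one direction and mask the more reactogenic group.* The required call follows severe entries or high fever, but the SAP rule covers any confirmed error, and investigators review all diary data. Removing a false severe entry also corrects overstatement.
- *Every unresolved entry should count as a reaction.* That would turn accidental entries into events.

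**Conclusion.** The point holds as a defect in a stated derivation rule. Followed literally, the SAP can score a real, mis-graded or mis-sized local reaction or non-fever systemic event as absent when no other day and no AE CRF record carries it. Otherwise it can misstate severity, onset or duration. This rests on reading a dropped value as a missing item, which is the natural reading but is not written out.

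The frequency is unknown and probably low. For the composite of any local reaction, a participant is lost only if all three items are otherwise no or missing across the seven days, which makes that loss rarer still. This is a cheap improvement to a primary safety summary, not a threat to the trial's conclusions.

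**What to change.** In SAP 3.1.3 and 6.1.3.1, and so in 6.1.6, extend the fever rule to all local reactions and systemic events:

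- If the site contact confirms an entry error and establishes the true value, transcribe that value through the data-handling memo and analyse it for that day. The value is no if no reaction occurred.
- If the contact confirms that a reaction occurred but its grade cannot be established, count it as present with severity missing.
- If it cannot be established whether any reaction occurred, leave the item missing and list the case.
- Flag every corrected entry, because some will rest on short-term telephone recall.

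The cost is a few SAP sentences, a few memo lines and one flag variable. The contact is already made and recorded; sites need only be told to note the true grade or size when they record it.
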